### 17.2.3 Exploratory Objectives

To explore cellular and humoral responses to Pfs230D1M (All Arms except Arms 4a/4b)

To identify host and parasite factors associated with transmission (All Arms)

To track transmission of parasites from human to human using highly variant gene fragments (All Arms)

GEE analyses with compound level clustering will be used to analyze ELISA, SMFA and safety endpoints.

## 17.3 Sample Size and Power Calculations

### 17.3.1 Pilot Study

#### 17.3.1.1 Safety

The arms are sufficiently sized for safety. For each dose level ( $n=15$ ) in Arms 1a, 2a, vaccination of 15 subjects gives a probability of at least 0.90 for detecting 1 or more serious or severe AEs that occur with a probability of 0.142 or more per subject.

If we combine all treated groups (arms 1a and 2a), 30 subjects, we have 95% power to detect 1 or more serious or severe AEs that occur with a probability of 0.095 or more per subject. Due to arms having different age ranges, this analysis would only be done to catch an AE that transcended these discrepancies.

We will compare all AE event proportions between the control arm and treated arm by Fisher's exact test.

#### 17.3.1.2 ELISA Analysis

There are several questions of interest based on the antibody response information to include the change in ELISA values from baseline after a given number of doses of vaccine and the change in ELISA values between doses. For this we will use age-group-specific WSRT within the 15 subjects receiving a given vaccine regimen.

The data from Protocol #17-I-N006 on subjects who had Pfs230 ELISA measurements after receiving two doses allow us to estimate the standard deviation (SD) of the log transformed Pfs230 ELISA responses at baseline (mean 3.688401 sd 0.5490291) and 3 months post vaccination 2 (mean 5.356736 sd 0.8868963).

Assuming similar values in this trial, there would be over 0.99 power to detect the difference between baseline and 3 months post-vaccination 2. This approximate power is calculated counting the number of significant comparisons out of a thousand comparisons between random normal draws from  $N(3.68, 0.55)$  and  $N(5.36, 0.88)$  using the Wilcoxon test.

Using the background information from #17-I-N006, we have greater than 80% power to reject a 2-sided 0.05 level WMW test if the geometric mean Pfs230 ELISA baseline level was 2.3-fold higher geometric mean than the level of detection in the vaccinated group post vaccination 2 (Note: 2.3-fold is lower than the 5.31-fold observed in #17-I-N006, so we treat these numbers as conservative). This approximate power is calculated counting the number of significant comparisons out of a thousand comparisons between random normal draws from  $N(3.68, 0.55)$  and  $N(3.68 + \log(2.3), 0.88)$  using the Wilcoxon test.

### 17.3.1.3 SMFA Analysis

For a group of 15 participants we anticipate at least 60% power to detect a difference in TRAs of 32% (the observed difference in #17-I-N006) and 80% power for a 40% difference. These Power calculations come from a simulation assuming values similar to the SMFA data from Protocol #17-I-N006, where the control group had an average TRA of 38 (sd 39) and a treatment group with sd 34. Thus counting the number of significant comparisons out of a thousand comparisons between random normal draws from  $N(38,39)$  and  $N(38+40, 34)$  using the Wilcoxon test can give approximate power.

If TBAs are used, we will standardize the TBAs to a common target control mean first using the methods of Swihart, Fay, & Miura (2018). A nice feature of the standardized TBA is that its power is identical to those of the TRA.

## 17.3.2 Main Study

### 17.3.2.1 Vaccine Activity

Vaccine activity will be measured by DSFs in children 9-18 years of age. The Bancoumana Community Study assessed monthly DSFs in children 10-18 years of age from March to August with a seasonal DSF positivity rate (i.e. at least 1 positive DSF) of 6%. We anticipate that this seasonal DSF rate will be increased to 12-16% for children 9-18 years of age during the rainy season with twice-monthly DSF testing. Doneguebougou has 560 children 9-18 years of age. We conservatively estimate that about 400 of these will be randomized and not drop out of the study.

Since the study is randomized by compound, clustering due to compound needs to be addressed in the power calculations. The Bancoumana Community Study provided data on seasonal parasitemia positivity which we use as a proxy for seasonal DSF positivity. For parasitemia, the intra-compound-correlation (ICC) was estimated to be .01 using a beta-binomial model. This low ICC coupled with the large number of compounds and relatively small number of subjects 9-18 years of age per compound (median of 4) indicates that clustering will be negligible. Power was simulated for a study with 100 compounds and 400 subjects with monthly DSF testing for 4 months. Since testing will be twice-monthly, simulating monthly testing will be conservative. The intra-subject correlation (ISC) for monthly serial DSFs was estimated to be .14 using a beta-binomial model for children 10-18 years of age from the Bancoumana Community Study. Four months of DSFs per child were generated using a beta-binomial model with  $ISC=.14$  and parameters chosen to achieve seasonal DSF positivity rates of 12-16% and seasonal vaccine activities (VAs) for the probability of a positive DSF of .50 or .60. A GEE model with compound level clustering and the number of positive DSFs as outcome was used for analysis. Ten

thousand clinical trials were simulated. Powers are provided in **Table 17** and **Table 18** which indicates we have power greater than .80 for scenarios with a seasonal DSF rate of 12-16%.

[figure not shown]
Data collection for the Age DE study during the 2019 season was encouraging for achievement of the primary endpoint, positive Direct Skin Feeds. As of March, there were 45 unique individuals with a positive DSF of the 369 participants monitored for this endpoint in the 9-18 year old cohort.

Our initial sample size for the power calculations for the VA in the Main Study was based on an assumption about seasonal infection rates ranging from 0.12-0.16 and power to reject a null hypothesis of no difference in rate of DSF positivity by arm is ultimately a function of the overall rate of DSF positivity and the true vaccine activity (**Table 17**). The current data indicates that the seasonal infection rate for the period monitored by DSF was 12% which was below the desired power threshold of 0.8.

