**Table 7. Summary of Study Progress for 19-I-N086**

	Pilot Phase		Main Phase			
	Arm 2a/2b 5-8 yo	Arm 1a/1b 9-18 yo	Arm 3a/3b 5-8 yo	Arm 3c/3d 9-18 yo	Arm 3e/3f ≥19 yo	Arm 4a/4b 1-4 yo
Number subjects enrolled	30	30	185	369	495	192
Timing of enrollment	May 2019	Apr 2019	Jun to Sep 2019			Aug to Nov 2019
Number subjects received ≥1 vaccine	30	30	183	368	490	--
Timing of vaccination	May to Oct 2019	Apr to Sep 2019	Jun to Nov 2019			--
Number subjects AL dosed prior to Vax #3	29	--	181	--	--	--
Timing of AL dosing prior to Vax #3	Aug to Oct 2019	--	Aug to Nov 2019	--	--	--
Number subjects underwent DSF ≥1	--	26	--	358	--	--
Timing of start -end of DSFs	--	Sep to Dec 2019	--	Sep 2019 to Mar 2020	--	--

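### The single-season DSF power claim (above 0.80 at rates of 12-16%) is not in the tables it cites, sits beside a statement that 12% fell short, and fails at vaccine activity 0.5

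*Combined protocol and SAP*

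**What the plan says.** Section 17.3.2.1 starts from a source study with a "seasonal DSF positivity rate (i.e. at least 1 positive DSF) of 6" per cent and anticipates 12-16% in this trial. It then describes the calculation: "Power was simulated for a study with 100 compounds and 400 subjects with monthly DSF testing for 4 months". For repeated feeds on the same child, "The intra-subject correlation (ISC) for monthly serial DSFs was estimated to be .14 using a beta-binomial model". For clustering, using parasitemia as a proxy, "the intra-compound-correlation (ICC) was estimated to be .01 using a beta-binomial model", and the effect is called negligible. VA is set at 0.50 or 0.60, and the analysis is a GEE on the number of positive feeds with compound-level clustering. Results are said to be in Tables 17 and 18, "which indicates we have power greater than .80 for scenarios with a seasonal DSF rate of 12-16" per cent.

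The text then turns to Year 1: "there were 45 unique individuals with a positive DSF of the 369 participants monitored for this endpoint". The following paragraph says that "the seasonal infection rate for the period monitored by DSF was 12% which was below the desired power threshold of 0.8". Table 17 gives the DSF-positive children needed for 0.8 power as 115, 64 and 40 at VA 0.4, 0.5 and 0.6. The section closes by calling for a second year and pooling the endpoints of both years.

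**The concern.** This is the power statement for the primary endpoint, and as printed a reader cannot verify it or reconcile it with its neighbours. The tables it cites hold something else. The paragraph after it says the bottom of the same range was not enough. It carries no VA condition, so it reads as covering both simulated effects. Anyone judging whether one season could have answered the primary question at VA 0.5 would be misled.

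**Working it through.** **1. The cited tables.** Table 17 keeps a title referring to seasonal DSF rates, but its cells are counts of positive children for 0.8 and 0.9 power. Table 18 gives blood-smear sample sizes at 70% background infection. Neither shows DSF power by seasonal rate.

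**2. The claim against Table 17.** Inputs: 400 children, taken as 200 per arm because Section 17.4 plans similar numbers of vaccine units per group.
- Overall rate r: expected positives = 400 × r, so 48, 56 and 64 at 12, 14 and 16%.
- Control-arm rate r: expected positives = 200 × r × (2 − VA), so 36, 42 and 48 at VA 0.5, and 33.6, 39.2 and 44.8 at VA 0.6.

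At VA 0.5 Table 17 needs 64. The overall reading meets this only at 16%, where power equals 0.80, and the control-arm reading never does. At VA 0.6 Table 17 needs 40. The overall reading meets this throughout, and the control-arm reading only at 16%.

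Table 17 itself is roughly right at these effects. The Schoenfeld count 4 × (1.96 + 0.84)² / (ln(1 − VA))² gives 66 at VA 0.5 and 38 at VA 0.6, against 64 and 40 printed.

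**3. The simulation.** Inputs from Section 17.3.2.1: 100 compounds, 400 children, four feeds each, ISC 0.14. Assumed because not stated: 50 compounds of four children per arm, two-sided 0.05, VA acting on the seasonal probability, ICC 0. The text under Table 17 prints alpha as 0.5 and the type 1 error rate as 0.8, which cannot be meant; Section 17.3.2.2 uses 0.05 two-sided.

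On the overall reading the control-arm rate is 2r / (2 − VA). At VA 0.5 and r = 12% this gives 16% against 8%. The per-feed probability was solved so that the beta-binomial chance of at least one positive in four feeds matches each arm's rate. The test is the log ratio of positive feeds with a compound-level sandwich variance, with at least 10,000 trials per cell. Rejection under the null was 0.053. Results from separate runs agree to about 0.01.

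| Rate read as | VA | 12% | 14% | 16% |
|---|---|---|---|---|
| Overall | 0.5 | 0.65 | 0.73 | 0.80 |
| Control arm | 0.5 | 0.51 | 0.59 | 0.65 |
| Overall | 0.6 | 0.85 | 0.92 | 0.95 |
| Control arm | 0.6 | 0.69 | 0.77 | 0.83 |

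**4. Closed-form check.** Two proportions, 200 per arm, VA 0.5, overall 12% (0.16 against 0.08):
- Null SE = √(2 × 0.12 × 0.88 / 200) = 0.0325.
- Alternative SE = √((0.16 × 0.84 + 0.08 × 0.92) / 200) = 0.0322.
- z = (0.08 − 1.96 × 0.0325) / 0.0322 = 0.51, so power is 0.69.

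The same formula gives 0.77 at 14% and 0.83 at 16%.

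**5. Other choices, VA 0.5, overall rate at 12/14/16%.**
- One-sided 0.05: 0.77/0.83/0.88.
- Binary GEE, two-sided: 0.69/0.77/0.84.
- Eight feeds at the same seasonal rate: 0.60/0.68/0.74.
- VA acting per feed: 0.62/0.69/0.75.
- ICC 0.01: 0.61 at 12% and 0.76 at 16%.

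The highest value found at 12% was about 0.80 (0.795, two-proportion formula, one-sided), so nothing exceeded 0.80 there.

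**6. Year 1.** With 45 positives, the event approximation z = (√45 / 2) × |ln(1 − VA)| − 1.96 gives 0.36 at VA 0.5 (power 0.64) and 1.11 at VA 0.6 (power 0.87).

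On the denominator, Table 7 shows 369 as enrolment in Arms 3c/3d. Its row "Number subjects underwent DSF ≥1" shows 358 of these plus 26 pilot children, 384 in all. Section 3.3.3 reports 2,875 feeds. At the cap of eight per child in Section 12.6.4, 358 children could supply at most 358 × 8 = 2,864, so pilot children are included. The rate is 45/384 = 11.7%, against 45/369 = 12.2%.

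**The case against.** The strongest reply is that the sentence looks like a leftover from an earlier power table and that the text following it already corrects it. The plan calls 12-16% the basis of its initial sample size, says 12% fell short, gives event targets instead, and adds a season. That stands. A reader might infer that the primary analysis as now planned is underpowered because of this sentence; the documents do not support that, since the planned analysis combines both years and does not rest on the single-season figure.

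A reader might also infer that the claim fails for every scenario, or that the two paragraphs contradict each other outright. Neither follows. The later paragraph speaks of the overall rate of DSF positivity, which favours the overall reading, and on that reading the claim is right at VA 0.6. The 45 positives in Year 1 also exceed the 40 that Table 17 needs there. Because neither statement names a VA, the conflict is between two unconditioned statements.

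The simulation description leaves alpha, sidedness, rate definition and compound sizes open, so no re-calculation can claim to be the sponsor's own. With a one-sided test, 14% and 16% pass at VA 0.5 on the overall reading. At 16% the two-sided count analysis is a tie with 0.80, and the binary analysis passes. None of these choices takes 12% above 0.80.

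Finally, the Year 1 denominator might look like a material misreport. It is not: 11.7% and 12.2% both round to 12%, and an intention-to-treat count could use 399 from Table 12 (45/399 = 11.3%). No conclusion changes.

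**Conclusion.** The statement is wrong as written for the primary endpoint. At VA 0.5 it is not met at 12% or 14%, and at 16% it is at best equalled on the overall reading. The shortfall at 12% is about 0.15 on the overall reading and 0.29 on the control-arm reading. At VA 0.6 it is correct only if 12-16% is the overall rate; otherwise it fails at 12% and 14%.

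The power figures assume two-sided 0.05, equal arms, four children per compound, VA on the seasonal probability and no compound correlation; an ICC of 0.01 lowers them by roughly 2 to 5 points. The table mismatch and the comparison with 64 needed positives do not depend on the simulation. The consequence is limited to an incorrect and untraceable power statement, because the plan has already moved to a two-year analysis.

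**What to change.** Delete the sentence, or limit it to VA 0.6 with 12-16% defined as the overall rate. State which rate is meant and correct the printed alpha and type 1 error rate. Give single-season power by rate and VA, and correct the references to Tables 17 and 18. Say plainly that at the Year 1 rate VA 0.5 did not have 0.80 power, and that this is why Years 1 and 2 are combined.

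As a minor item, define who counts as monitored in Year 1 and reconcile 369 with the 384 children fed in Table 7.

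The cost is a re-run of an existing simulation and some wording, with no change to design, conduct or analysis. The single-season figure becomes less favourable.

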**Table 17. Sample Size Power Calculations Based on Seasonal DSF Infection Rates and Seasonal Vaccine Activity**

Power	Number of DSF+ Individuals Needed		
	VA = 0.4	VA = 0.5	VA = 0.6
0.8	115	64	40
0.9	153	87	53

As we remain blinded, we simulate power under three different scenarios for vaccine activity (**Figure 32**). In the first scenario, we assume that vaccine activity is 0.4. In this simulation, 115 unique individuals would need to experience a DSF+ in order to reject the null hypothesis of no difference at alpha= 0.5 with a type 1 error rate of 0.8. In the scenario of 0.5 vaccine activity, 64 unique individuals would need to experience a positive feed. In the scenario with 0.6 VA, 40 unique individuals would need to experience a positive feed to achieve 0.8 power.

**Figure 32. Simulated power under assumptions of 0.4, 0.5, and 0.6 vaccine activity.**

These simulations would indicate that a second year of study is required in order to capture more of the seasonal infections, as the DSFs were monitored only from September – March. To guard against scenarios in which the VA falls in the lower ranges, we intend to combine the endpoints from Year 1 and Year 2 to achieve the needed power to distinguish vaccine activity. With additional follow up time, it appears feasible to have power for the all above scenarios.

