### 17.3.2.2 Vaccine Efficacy

Vaccine efficacy will be measured by blood smear (BS) and detection of asexual Pf parasitemia. The background infection rate in the population is measured as the proportion of individuals from a recent PfSPZ trial (NIAID Protocol #16-I-N004) with any BS+ during follow up. Using this as the rate of background infection we can calculate power under various scenarios using as endpoint parasitemia positivity over the season. We use simple binomial tests with  $\alpha = .05$  two-sided and ignore the anticipated negligible effects of compound level clustering. Sample sizes are multiplied by an inflation factor of two to adjust for potential compound level contamination of the vaccine effects due to mixing of mosquitoes or movement of vaccinees. We see that with a minimum of 350 total subjects 1-8 years of age that are randomized and do not drop out, we have power to detect VEs of 30% or greater within this age group alone based on the risk of first infection. We will analyze subjects 9-18 years of age based on the proportion of positive blood smears.

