### 17.3.2.3 Analysis

The primary DSF analysis will use a GEE model with compound level clustering and the number of positive DSFs as outcome will be used for analysis with an offset for the number DSF tests. The primary parasitemia analysis will be analogous. The primary analysis population will follow the intention-to-treat principle. Additional analyses will explore the effects of different covariates such as time since start of the rainy season, SMC treatment, compound-level vaccine coverage, or proximity to a control compound on vaccine efficacy.

The primary safety and immunogenicity analyses will compare the rates of AEs or levels of antibody/activity between vaccinated and control individuals using standard statistical methods that respect compound-based randomization, as appropriate.

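### The power statement for the primary skin-feed endpoint has misprints and a contradiction, is not shown for the declared count analysis, and does not support adequate power at a vaccine activity of 0.4

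*Combined protocol and SAP*

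**What the plan says.** **Primary analysis.** Section 17.2.1 names a Poisson GEE with an offset for feeds performed. The any-positive proportion is a separate binary GEE. Section 17.3.2.3 repeats: "The primary DSF analysis will use a GEE model with compound level clustering and the number of positive DSFs as outcome".

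**Planning claim.** Section 17.3.2.1 simulated 400 children in 100 compounds with four monthly feeds, for VA of .50 or .60, and states that "we have power greater than .80 for scenarios with a seasonal DSF rate of 12-16" per cent.

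**After Year 1.** The same section then reports that "the seasonal infection rate for the period monitored by DSF was 12% which was below the desired power threshold of 0.8".

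**Table 17.** The requirement is given in unique DSF-positive individuals. For power 0.8 it is 115, 64 and 40 at VA 0.4, 0.5 and 0.6. For power 0.9 it is 153, 87 and 53. The text beneath says "115 unique individuals would need to experience a DSF"-positive result at VA 0.4 "in order to reject the null hypothesis of no difference at alpha= 0.5 with a type 1 error rate of 0.8".

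**Conclusion.** Years 1 and 2 will be combined, and "With additional follow up time, it appears feasible to have power for the all above scenarios".

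**The concern.** The requirement is expressed in children with any positive feed, but the primary outcome counts feeds. A few children contribute several positive feeds each. That overdispersion lowers the information per positive child in a count analysis but not in an any-positive analysis, so Table 17 may not describe the test that will be run.

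The all-scenarios conclusion comes with no Year 2 rate, no projected number of positive children, and no rule for a child who is positive in both years. Two sentences in the same section disagree on whether 12% positivity is enough, and the significance level is misprinted.

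This is the power statement for the only main-phase primary endpoint, and it is the reason given for the second season. If true activity is near 0.4, a null result would be read against a power the design has not been shown to have.

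**Working it through.** **Inputs.** Section 17.3.2.1: intra-subject correlation (ISC) 0.14; 400 children in 100 compounds; 45 positive of 369 monitored in Year 1. Section 3.3.3: 70 positive feeds of 2875, a per-feed rate of 0.0243. Table 7: 26 + 358 = 384 children fed at least once. Section 12.6.4: 8 feeds in Year 1, 10 in Year 2. Section 8.3: no new enrolment. Assumed: two-sided alpha 0.05 and equal arms.

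**1. Reproducing Table 17.** I simulated beta-binomial feeds with ISC 0.14 and a compound-robust Wald test, setting the expected number of positive children to Table 17's values. Power:

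| Analysis, feeds, VA reading | 115 (VA 0.4) | 64 (0.5) | 40 (0.6) | 153 (0.4) | 87 (0.5) | 53 (0.6) |
|---|---|---|---|---|---|---|
| Any-positive, 4, per feed | 0.815 | 0.791 | 0.798 | 0.909 | 0.905 | 0.903 |
| Any-positive, 8, per feed | 0.790 | 0.789 | 0.802 | 0.891 | 0.893 | 0.900 |
| Count, 4, per feed | 0.807 | 0.760 | 0.749 | 0.923 | 0.888 | 0.867 |
| Count, 8, per feed | 0.734 | 0.699 | 0.693 | 0.876 | 0.830 | 0.814 |
| Count, 8, seasonal | 0.848 | 0.746 | 0.724 | 0.971 | 0.895 | 0.851 |

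The any-positive analysis with VA read per feed matches all six cells within 2 points. No count variant matches all six. With the actual 8 feeds, the count GEE at Table 17's 0.8 numbers gives about 0.69–0.73 (0.68 at the lowest in a second run) with VA per feed, or 0.72–0.85 with VA seasonal. Moving from 4 to 8 feeds at a fixed number of positive children lowers count-GEE power, so simulating monthly feeds is not conservative for this outcome.

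**2. The 12–16% claim.** 12% × 400 = 48 and 16% × 400 = 64. Table 17 needs 64 at VA 0.5 for power of just 0.80. Count-GEE power with 4 feeds, per-feed VA and the rate taken as pooled over arms:
- VA 0.5: 0.62 at 12%, about 0.75 at 16%.
- VA 0.6: 0.83 at 12%, 0.93 at 16%.

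If the rate means the control arm, these fall to 0.48 and 0.62 for VA 0.5, and to 0.66 and 0.81 for VA 0.6.

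**3. Positive children after two seasons.** Let r be the Year 2 positivity.
- Unique children, years independent: 45 + (369 − 45)r = 45 + 324r, which is 84 at 12% and 97 at 16%.
- Counting a child once per season: 45 + 369r, which is 89 at 12% and 104 at 16%.
- Year 1 per-feed rate, 384 children, the same children remaining infectious: about 72–77 unique. With independent years: about 94–98.
- Rate needed for 115: (115 − 45)/324 = 21.6% new children, or (115 − 45)/369 = 19.0% counting person-seasons. Year 1 gave 45/369 = 12.2%.

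**4. Two-year power of the count GEE at the Year 1 rate.** Var(log rate ratio) ≈ φ(1/E_control + 1/E_vaccine). Each arm has 192 × 18 = 3456 feeds. For VA 0.4 the control rate is 0.0243 × 2/1.6 = 0.0304, giving about 105 positive feeds against 63.
- Child propensity fully persistent: φ = 1 + 17 × 0.14 = 3.38. SE = √(3.38 × (1/105 + 1/63)) = 0.293; z = 0.511/0.293 = 1.74; power = Φ(1.74 − 1.96) ≈ 0.42.
- Years independent: φ = (8 × 1.98 + 10 × 2.26)/18 = 2.14. SE = 0.233; z = 2.19; power ≈ 0.6.

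The same formula at VA 0.5 gives about 0.64 and 0.83. Simulation gives 0.43–0.62 (VA 0.4), 0.66–0.86 (VA 0.5) and 0.86–0.97 (VA 0.6). Using the step 3 totals instead, at 84–104 positive children and VA 0.4, count-GEE power is 0.49–0.79 across 8- and 18-feed models and both readings of VA.

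**The case against.** The strongest reply is that Year 2 need not resemble Year 1. Year 1 feeds ran from September to March, while Section 9.1 puts transmission at June to December. The Protocol Summary plans Year 2 dosing for June to October 2020, and there are 10 feeds rather than 8. In the Phase 1 adult trial (Section 3.2.4) positive feeds rose from 0.82% to 1.74% between years. If the Year 2 per-feed rate were 1.5 times that of Year 1, independent years would give about 115 unique children. At 2.1 times, count-GEE power at VA 0.4 would be 0.82 (0.64 if the same children stay infectious). This stands: a reader might infer that VA 0.4 is out of reach even with two years, and the documents do not show that. But the protocol states no such Year 2 rate. Unique positives in the adult trial rose only from 19 to 25, with 12 weeks of feeding in the first year and 16 in the second (Table 6). Applied here, 45 × 25/19 = 59, and 45 + 59 = 104 is still below 115.

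Second, it is tempting to say that Table 17 was certainly built on the any-positive analysis. That is inferred from fit. The code and Figure 32 are not available, the only simulation described in 17.3.2.1 used the count outcome, and the 4-feed count model gives 0.807 at the VA 0.4 cell. The inference needs VA read per feed, whereas the table title speaks of seasonal activity. On the seasonal reading neither analysis fits all six cells, and the any-positive analysis would reach 0.82–0.85 at 97–104 positive children for VA 0.4. That analysis is not the primary one.

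Third, the alpha misprint might be read as meaning the simulation ran at 0.5. It did not: the same paragraph speaks of 0.8 power, Section 17.3.2.2 uses .05 two-sided, and Table 17 reproduces at 0.05. The 12–16% sentence is leftover text that the next paragraph contradicts, and it did not drive the Year 2 decision.

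**Conclusion.** The power statement needs correcting in four places.

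- The significance level and power are misprinted.
- The claim of power above 0.80 at 12–16% fails for VA 0.5 and holds only for VA 0.6, with the rate pooled over arms.
- Table 17 is best explained by the any-positive analysis and overstates count-GEE power in most cells under the actual schedule. On the seasonal reading of VA, the VA 0.4 cell is an exception at 0.85.
- Feasibility for all scenarios is unsupported at VA 0.4 on the protocol's own rates. VA 0.5 is borderline and VA 0.6 adequate.

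The two-year figures assume the Year 1 per-feed rate, ISC 0.14, 384 children and complete follow-up. Each range runs from full persistence of a child's infectiousness across years to independence between years. Compound correlation of 0.01 was not added; its effect is small (design effect about 1.03). The documents do not support saying that the trial is underpowered throughout, or that VA 0.4 cannot be reached.

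**What to change.** In Section 17.3.2.1:

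1. Print two-sided alpha 0.05 and power 0.80.
2. Delete the 12–16% sentence, or limit it to VA 0.6 and say whether the rate is pooled or control-arm.
3. Define VA as per-feed or seasonal, and state how a child positive in both years is counted.
4. Label the analysis behind Table 17, and re-run the existing simulation for the primary count GEE with 8 + 10 feeds.
5. Replace the all-scenarios sentence with projected power by VA under a stated Year 2 rate, noting that VA 0.4 is not powered at 12–16%.

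The cost is revised wording and one simulation run. The primary analysis stays as declared and no participants are added. The only downside is a less favourable stated power.

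### The two-year power claim in Section 17.3.2.1 is not supported by the plan's own rates at vaccine activity 0.4

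*Combined protocol and SAP*

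**What the plan says.** Section 17.3.2.1 gives three statements about power for the primary DSF endpoint.

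- **Original design.** Simulations for VA 0.5 and 0.6 with about 400 children are summarised as tables "which indicates we have power greater than .80 for scenarios with a seasonal DSF rate of 12-16" per cent.
- **After Year 1.** "As of March, there were 45 unique individuals with a positive DSF of the 369 participants monitored for this endpoint". The text describes the Year 1 rate as "12% which was below the desired power threshold of 0.8".
- **Table 17 and the pooled plan.** At VA 0.4, "115 unique individuals would need to experience a DSF+ in order to reject the null hypothesis". "In the scenario of 0.5 vaccine activity, 64 unique individuals would need to experience a positive feed". At VA 0.6, "40 unique individuals would need to experience a positive feed to achieve 0.8 power". The 0.9-power row reads 153, 87 and 53. Below Figure 32 the plan proposes to pool the two years as protection against low VA, and concludes "With additional follow up time, it appears feasible to have power for the all above scenarios".

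No Year 2 positivity rate, retention, rule for children positive in both years, or projected two-year total is given. Section 8.3 allows no new enrolment in Year 2. Section 12.6.4 sets 8 feeds after dose 3 and 10 after dose 4.

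**The concern.** The second season is argued for as insurance against lower VA, and VA 0.4 is the lowest scenario in Table 17. If the pooled data are unlikely to bring 115 unique positives, the insurance is weakest where it is invoked. A colleague planning the analysis, or reading a non-significant primary result, could then take it that VA 0.4 had been tested with at least 0.8 power. The plan sets no such interpretation itself, but this sentence is what such a reading would rest on.

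**Working it through.** **Inputs.** Required positives 115 / 64 / 40 (Table 17). Year 1: 45 positive of 369 (Section 17.3.2.1), and 70 positive feeds of 2875 (Section 3.3.3). Seasonal range 12 to 16%, planned 400 children and intra-subject correlation 0.14 (Section 17.3.2.1). I read the printed alpha of 0.5 and type 1 error rate of 0.8 as two-sided alpha 0.05 and power 0.8; a literal alpha of 0.5 would need only 36 events. Allocation is taken as 1:1.

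**1. Reproducing Table 17.** Events = 4(1.96 + 0.842)² / [ln(1 − VA)]² = 31.4/0.261, 31.4/0.480 and 31.4/0.840, or 121, 66 and 38 after rounding up. The same approximation gives power 0.782, 0.792 and 0.826 at 115, 64 and 40. A 20,000-run simulation with 200 children per arm and a Poisson-variance Wald test gave 0.811, 0.786 and 0.792. Table 17 is therefore a fair 0.8 benchmark. The curves in Figure 32 were not available to this check.

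**2. Power at other counts.** With E positives against Table 17's requirement D: power = Φ(2.802 × √(E/D) − 1.96).

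**3. What Year 2 must supply at VA 0.4.** 115 − 45 = 70. That is 70/400 = 17.5% or 70/369 = 19.0% if nobody is positive in both years. If the seasons are independent and repeaters count once, it is 70/355 = 19.7% or 70/324 = 21.6%.

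**4. What Year 2 might supply (369 to 400 children, full retention).**

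| Year 2 assumption | Two-year unique positives | Power at VA 0.4 |
|---|---|---|
| 12%, no repeats | 45 + 44 = 89 to 45 + 48 = 93 | 0.69–0.71 |
| 16%, no repeats | 45 + 59 = 104 to 45 + 64 = 109 | 0.76–0.78 |
| Year 1 rate stretched to 10 feeds, no repeats | 96–101 | 0.73–0.75 |
| 16% stretched to 10 feeds (18–20%), no repeats | 112–125 | 0.79–0.83 |
| 12%, independent seasons, repeaters once | 84–88 | 0.67–0.69 |
| 16%, independent seasons, repeaters once | 97–102 | 0.73–0.75 |
| 20%, independent seasons, repeaters once | 110–116 | 0.78–0.80 |
| Year 1 rate, child propensity persists | 70–76 | 0.59–0.63 |
| 16% rate, child propensity persists | 91–98 | 0.70–0.73 |

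The persistence rows use a beta-binomial with correlation 0.14. Matching 45/369 over 8 feeds gives a mean of 0.0238 per feed and a 0.190 chance of at least one positive in 18 feeds; 0.190 × 369 = 70.

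**5. VA 0.5 and 0.6.** Even 70 positives exceed 64 and 40. At VA 0.5 power is Φ(2.802 × √(70/64) − 1.96) = 0.83, although the margin is only 6 children before any Year 2 loss.

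**6. The other two statements.** At 12% of 400 there are 48 positives. VA 0.5 needs 64, so power is Φ(2.802 × √(48/64) − 1.96) = 0.68, not above 0.80. In the other direction, the 45 positives seen in Year 1 already exceed the 40 needed at VA 0.6, so calling 12% below the threshold does not hold there.

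**7. The planned primary analysis.** Sections 17.2.1 and 17.3.2.3 specify a GEE on the number of positive feeds, not on unique positive children. Simulating it at Year 1 rates (384 children, 100 clusters, 70/2875 = 2.4% per feed, correlation 0.149 fitted to Year 1, an assumed 7 + 9 attended feeds, arm-specific beta-binomial means) gave power of about 0.42–0.57 at VA 0.4 and 0.63–0.82 at VA 0.5. The lower ends have child propensity persisting across years; the upper ends have independent seasons. Modelling the vaccine effect differently within children would move these figures, so they are indicative only.

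**The case against.** The strongest reply is that the sentence is hedged and gives no power figure, and that 115 is not out of reach. Year 2 has 10 feeds against 8, and 16% scaled to 10 feeds gives totals of 112 to 125. Year 1 feeds ran only from September to March, whereas fourth doses were planned for June to October 2020, so Year 2 may cover more of the season. The original design addressed only VA 0.5 and 0.6, and both meet their 0.8 targets. The figure 115 also depends on method: a simple per-child comparison of proportions, ignoring clustering, would need about 93 to 95.

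Much of this stands. A reader might infer that the plan cannot supply 115 positives, that 16% of the 384 children fed (45 + 61 = 106) is a ceiling, or that the trial has no useful power. The documents support none of these.

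It does not rescue the sentence. Reaching 115 takes the top of the range, scaling for the extra feeds, full retention and almost no repeat positives together, and the plan states none of these. The season argument carries no figure, and the 12 to 16% range was already set for the rainy season with twice-monthly feeds. Year 1's 2.4% per feed was close to the 2.5% or higher that Section 4 expects. At 2.5%, 384 × 10 feeds gives 96 positive feeds, or about 62 children at Year 1's ratio of 45 to 70: a total of about 107 before repeats or dropout. The 115 is the plan's own benchmark, and the simpler per-child test is not its primary analysis.

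The 0.9-power row (153) should not be held against the plan, since it names 0.8 as its threshold.

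**Conclusion.** Wrong as written, but limited in reach. Feasibility for all scenarios is not supported at VA 0.4, where power on the Table 17 scale is about 0.69 to 0.78 at the stated rates with no repeats, and about 0.59 at Year 1 rates if child-level propensity persists. All of these assume full retention. The claim can be kept at VA 0.5 and 0.6 on that basis. The statement of power above 0.80 at 12 to 16% fails at VA 0.5 when the rate is 12%, and the below-threshold statement fails at VA 0.6. For the count-based primary analysis the indicative power is lower still under within-child correlation: about 0.4 to 0.6 at VA 0.4, and 0.6 to 0.8 at VA 0.5.

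The denominator 369 is the main-arm enrolment, while Table 7 shows 26 + 358 = 384 children with at least one feed. This is clerical: 45/369 = 12.2% and 45/384 = 11.7% both round to 12%.

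**What to change.** In Section 17.3.2.1:

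- Limit the 0.8-power statement for pooled Years 1 and 2 to VA of 0.5 or more, labelled as resting on Table 17's count of unique positive children.
- Say that power at VA 0.4 is expected to be about 0.6 to 0.78 on that basis, and give the assumed Year 2 rate, retention, handling of children positive in both years, and projected two-year total.
- Recompute power for the planned Poisson GEE on the number of positive feeds, with within-child correlation across both years, and report it beside the Table 17 figures.
- Limit the statements about power above 0.80 and below the threshold to the VA values that Table 17 supports.
- Correct the printed alpha and type 1 error, and the 369 denominator, as clerical items.

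The cost is revised wording and one simulation exercise. No participants, visits or procedures are added; the stated power becomes less favourable.
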